5. STUDY CONDUCT

5.1 Restrictions during the study

Restrictions regarding laxative use, restricted medications and requirements for change in the study drug dose are provided in Section 5.6

5.2 Subject enrollment, randomization and the initiation of the investigational product

5.2.1 Informed Consent Process

All patients consecutively admitted to the medical ICU service who are admitted to the MICU, CCU, SICU or NCCU at Tufts MC will be screened on a daily basis (through review of the ICU admission note, available laboratory data, the medication administration record, and the patient flowsheet by one of the study investigators who will determine if the patient meets all inclusion criteria and has no exclusion criteria participation in the study. An enrollment screening sheet (submitted to IRB) will be reviewed and signed by either [name], Dr. [name] or [name] before the patient/LAR is approached for consent.

For non-English speaking patients (legally authorized representatives) who are invited to participate in the study, and an IRB-approved Short Form consent exists for their language, the IRB-approved consent Short Forms per the IRB's Short Form policy will be used during the consent discussion.

Informed consent will be obtained by Drs. [name], [name], [name], [name], [name], or [name]. Approval will be obtained from the subject's Medical ICU attending physician before a consent discussion occurs. [name] is a critical care pharmacist researcher with more than 20 years of

Drug Substance: Movantik
Study Number: ESR-15-11000
Tufts IRB #12043
Version: Protocol version #19
Date: September 10, 2018

experience in obtaining patient consent from critically patients (or their legally authorized representatives). In the numerous ICU clinical trials he has served as a co-investigator/research coordinator at Tufts Medical Center he has led consent discussions for more than 400 patients. Over the past 6 months, [name] has been trained by Drs. [name] and [name] to conduct high quality consent discussions for this study. During March/April 2017, Drs. [name] and/or [name] carefully evaluated 5 different consent discussions conducted by [name] using an IRB-approved review metric and found that [name] can conduct high-quality consent discussions that meet all of the criteria of the Tufts MC IRB. Drs. [name], [name] and [name] will always ensure that [name] (or [name] or Dr. [name]) will always be available to participate in a consent discussion should questions (medical or otherwise) come up that [name], [name] or [name] feel he is not qualified to answer. Given Drs [name], [name] and [name]'s experience in consent discussions with ICU patients/their representatives, there are no plans to have the PI or a medical Co-I be present during all or part of the consent process unless the ICU patient (or their representative) have questions that [name], [name], or [name] cannot answer.

All patients will be evaluated by a member of the investigative team to determine if they have the mental capacity to provide consent for study participation. For the purposes of this study, a patient will be deemed to be cognitively intact if they have an ICDSC=0 (i.e. neither delirium nor subsyndromal delirium) and are not sedated. It is expected that the vast majority of patients will be not able to initially provide consent given their critical care illness and the use of scheduled opioids that have sedative properties. In addition, it is estimated that about two-thirds of the potential subjects will be mechanically ventilated and thus all be received sedative medications. Furthermore, close to 70% of patients of all patients admitted to the ICU have delirium or subsyndromal delirium, cognitive states that prevent obtaining consent from subjects. Drs. [name], [name], [name], [name], [name] and [name] will each be able to determine whether the subject is able to provide informed consent. As per the ICF, a legally recognized representative will be recognized in the following order: healthcare proxy (that is documented and verified) > spouse >adult child > parent of guardian > adult sibling.

Before the enrollment of a decisionally-impaired subject Drs. [name], [name], [name], [name], [name] and/or [name] will confirm that the study is not prohibited by law for this subject. The legally authorized representative will be contacted and invited to meet face-to-face with one of the investigators to provide written consent at Tufts Medical Center. Permission will be obtained from the primary provider for the participation of the patient in the study before the legally authorized representative is contacted. All consent discussions with a legally authorized representative will take place in location at Tufts MC that is both private and quiet (e.g., an ICU conference room). The legally authorized representative (or the patient) will be provided with a copy of the consent form to read and all questions will be answered prior to their signing the consent. All sections of the ICF will be carefully reviewed including the fact that the legally authorized representative is free to discontinue the participation of the subject at any time for any reason. No research related activities will occur prior to the consent being signed. The original signed ICF will be stored in the locked office of the investigator. A copy of the signed ICF will be given to the legally authorized representative and the methods (as outlined in the ICF) to research a member of the research team if they have additional questions will be emphasized. The investigator's recognize the potential vulnerability of the legally authorized representative in this setting (ie. having a relative who is critically ill) and thus will terminate the consent discussions in any situation where the legally authorized representative appears to be uncomfortable or apprehensive about providing consent for their relative to participate in the study. In an effort to help recognize situations where the legally authorized representative may be apprehensive about providing consent, written informed consent will be obtained in the presence of the patient's nurse. The patient's nurse is ideally suited to serve as a

Drug Substance: Movantik
Study Number: ESR-15-11000
Tufts IRB #12043
Version: Protocol version #19
Date: September 10, 2018

witness because they in fact may have met the legally authorized representative before. This procedure is frequently used for research studies in the ICUs at Tufts MC when consent is obtained from a legally authorized representative. The investigator conducting the consent discussion with the legally authorized representative will confirm with the legally authorized representative that the subject will be withdrawn from the study if they appear to be unduly distressed.

Telephone Consent:

In situations where it is not possible for the LAR to physically come to Tufts Medical Center for an in person consent discussion (for example, lives outside of Boston area, inclement weather, LAR's schedule, study consent time frame, etc.), Drs. [name], [name], [name] or [name] will conduct telephone consent:

- 1) E-mail, fax, (or mail) the ICF to the LAR. (If mailed, 2 copies will be mailed, so the LAR can keep a copy.)
- 2) The LAR will be instructed to contact Drs. [name], [name], [name] or [name] after reviewing the ICF.
- 3) The person consenting the LAR will have the same consent discussion via phone that they would have had in person (including asking questions to gauge comprehension and answering the LAR's questions)
- 4) A witness will be present during telephone consent (at Tufts Medical Center with the investigator conducting the consent process)
- 5) If the LAR consents, the LAR will complete and sign the ICF (in all appropriate sections) and either e-mail a scanned PDF, fax, (or mail) the signed and dated ICF to the research team.
- 6) The LAR should be instructed to keep one signed copy of the ICF for his/her own records.
- 7) Once the ICF (signed & dated by the LAR) is received by the research team, the Investigator who explained the study should sign the appropriate signature line with the current date (the date they receive the ICF and sign, not the date they consented the LAR).
- 8) Ensure all signatures and dates are accurately documented. Any errors should be noted in a note or memo to file.
- 9) Document in a separate note to file/progress note, or with a note under the PI signature line on the ICF that consent was obtained over the phone with the actual date and mailed/e-mailed/faxed back. For example "*Discussed with [LAR name] via telephone on [insert date], and received signed consent form on [insert date].*"

No study-related activities will be conducted prior to consent being obtained.

The investigative staff will regularly remind the ICU team that informed consent is indeed a process and that obtaining a signature on the ICF is part of that process. In all interactions with the subject (and their family) the investigative team will introduce ourselves so that the subject (and their family) can associate us with the study. We will also educate them on the study procedures as they progress. The trial requires that we explicitly interact with the subject through the study period. The patients cognitive status will be evaluated twice daily using the Intensive Care Delirium Screening Checklist (ICDSC) and their sedation level will be evaluated four times daily using the SAS. When subjects are deemed to have an ICDSC score = 0 (ie., neither subsyndromal delirium or delirium) and have a SAS of 4 (ie. are awake) they will be considered to potentially have the potential capacity of providing informed consent. It should be noted there are other reasons besides delirium and sedation that would make a subject incapable for re-consent

Drug Substance: Movantik
Study Number: ESR-15-11000
Tufts IRB #12043
Version: Protocol version #19
Date: September 10, 2018

other than delirium. The subject's clinical team will also be asked to determine if they are now relying on the subject for decision making capacity. Based on this process, on the day that the investigative team first determines that the subject has adequate decision making capacity to provide their own consent, the subject will be re-consented (in those situations where a legally authorized representative had originally provided consent). During this consent discussion the subject will be educated about the research that has been completed to date (in addition to what additional research activities lie ahead). If the subject does not wish to remain in the study, all study-related activities will stop and no research data collected to date will be used. This re-consent process and its result will be documented in the patient record.

5.2.2 Procedures for randomization

Subjects meeting all inclusion criteria and no exclusion criteria will be randomized by a pharmacist in the Tufts Medical Center investigational drug pharmacy to one of two study groups (ie. naloxegol or placebo) on the first day. Randomization (in blocks of 4) will take place by means of a computer-generated random-number table and will be developed by a pharmacist in the Tufts Medical Center investigational drug pharmacy. This randomization schedule will assign each subject a study number, which will be used to identify treatment allocation (ie. naloxegol or placebo) and all study data that is collected during the study.

5.3 Procedures for handling subjects incorrectly enrolled, randomized or initiated on the investigational product.

Both the investigative team and the research pharmacists in the investigational drug pharmacy have extensive experience in conducting randomized, double-blind, medication-based trials in the ICUs at Tufts Medical Center. An investigational screening sheet is always completed and verified by a secondary member of the investigative team before a patient/family is approached for consent and before randomization occurs. Should the very unlikely situation occur that a patient is mistakenly enrolled in the study or consent is withdrawn by the patient (family member), a member of the investigative team will contact the study PI, the patient's primary physician and the investigation drug pharmacy regarding this issue. In all situations the Tufts Med Center IRB and AstraZeneca will be informed of this occurrence in a timely fashion.

5.4 Blinding and procedures for unblinding the study

5.4.1 Methods for ensuring blinding

Subjects and all ICU caregivers will be unaware of the treatment assignments for the duration of the study. The fact that AstraZeneca will be providing "the official" Movantik 12.5mg and 25mg placebo tablets for use in the study make it next to impossible for either the clinical or investigative team to know whether active drug or placebo drug is being administered.

All investigators will remain blinded until the final study data set is analysed. The study biostatistician will complete all analysis (including that required for intermittent analysis by the DSMB using a group A vs. group B approach. The research pharmacist at Tufts Medical Center (or his/her designate) will have access to a computer randomization program in order to assign study treatment and he/she will be the only person who will have access to the treatment assignment group.

Drug Substance: Movantik
Study Number: ESR-15-11000
Tufts IRB #12043
Version: Protocol version #19
Date: September 10, 2018

5.4.2 Methods for unblinding the study

If needed for medical reasons, a member of the investigative team will contact the research pharmacist (or designate) on a 24/7 basis to unblind the patient. In this instance the research pharmacist will provide the treatment allocation to a member of the clinical team. The investigative team will remain blinded in all situations where a member of the clinical team is provided with the treatment allocation. Any episode of unblinding will be documented by the research pharmacist.

5.5 Treatments

5.5.1 Identity of investigation products(s)

The following investigative products will be used in this protocol:

Treatment:

Movantik 25mg tablet
OR

Movantik 12.5 mg tablet (for use in those situations where the protocol calls for the lower drug dose)

Control:

Placebo (Movantik) 25 mg tablet
OR

Placebo (Movantik) 12.5 mg (tablet) (for use in those situations where the protocol calls for the lower drug dose)

Naloxegol placebo tablets and naloxegol active drug tablets appear identical, even when crushed.

5.5.2 Doses and treatment regiments

Treatment arm:

Naloxegol 25 mg daily [administered orally (or enterally)]

A lower dose of naloxegol (12.5mg mg daily) will be administered in the following two situations:

- a. A patient who is receiving a moderate CYP3A4 inhibitor that includes diltiazem, erythromycin, fluconazole, or verapamil (at any dose)
- b. A patient with a calculated creatinine clearance (using the modified MDRD approach) ≤ 60 ml/min

This based on the following information included in the Movantik package insert:

Drug Substance: Movantik
 Study Number: ESR-15-11000
 Tufts IRB #12043
 Version: Protocol version #19
 Date: September 10, 2018

- 1 **Under drug interactions: The concomitant use of naloxegol and a moderate CYP3A4 inhibitor may increase naloxegol serum concentrations.** If use cannot be avoided, the dose of naloxegol should be reduced to 12.5mg daily. The investigators are hesitant to exclude all medical ICU patients receiving a moderate CYP3A4 inhibitors from the study given that the list of medications in this list is long and many are used with a high prevalence in the ICU (e.g. diltiazem, erythromycin, fluconazole, or verapamil). With a 12.5 mg naloxegol tablet (and matching placebo) available from AstraZeneca, it will be feasible to administer the lower 12.5 mg daily naloxegol dose to subjects with this potential interaction without compromise the rigor or blinding of the study.
- 2 **Under dosage and administration: The starting dose for patients with a creatinine clearance ≤ 60 ml/min is 12.5 mg daily.** This dose recommendation is based on the fact that some patients with a creatine clearance ≤ 60 ml/min who were exposed to naloxegol 25mg daily were shown to exhibit markedly higher systemic exposure to naloxegol compared to subjects with normal renal function. Given that naloxegol is metabolized through the cytochrome P450 system of the liver, the reason for these high levels is not understood. The investigators are hesitant to exclude all medical ICU patients with a calculated creatinine clearance ≤ 60 mL/min given that this population represents more than 50% of the medical ICU population. With a 12.5 mg naloxegol tablet (and matching placebo) available from AstraZeneca, it will be feasible to administer the lower 12.5 mg daily naloxegol dose to subjects with renal dysfunction without compromise the rigor or blinding of the study.

Note:

- Renal function often changes (either worsens or improves) during the ICU stay. Therefore, the creatinine clearance will be calculated daily. For a patient whose creatinine clearance drops to ≤ 60 ml/min during the study, the study drug dose will be reduced from 25mg daily to 12.5mg daily. For a patient whose creatinine clearance improves to ≥ 60 ml/min during the study, the study drug dose will be increased to 25 mg daily.
- It is possible that medications with moderate CYP3A4 activity may either be clinical required or stopped during the period of the study. If a patient requires the initiation of a medication with moderate CYP3A4 activity while receiving study medication (and other therapeutic alternatives without this property do not exist), then the study drug dose will be reduced to 12.5 mg daily. If a medication with moderate CYP3A4 activity is stopped during the period of study drug administration then the study drug dose will be increased to 25mg daily on the day after the CYP 3A4 moderate inhibitor is stopped.
- If a patient enrolled in the study requires a strong CYP3A4 medication (and another therapeutic alternative without this property does not exist), then the patient will be removed from the study.

Control arm:

AstraZeneca Naloxegol 25 mg placebo daily [administered orally (or enterally)]

A lower placebo dose of 12.5mg will be used for either of the above situations (ie. #1 or #2) where the 12.5mg daily dose is warranted.

Study drug administration:

If oral study drug medication is not possible (e.g. intubation) then the study drug will be administered via a gastric or enteral tube as recommended in the Movantik package insert. Tube feeds (if being

Drug Substance: Movantik
Study Number: ESR-15-11000
Tufts IRB #12043
Version: Protocol version #19
Date: September 10, 2018

administered) will be held for one hour and then the feeding tube will be flushed with 30 mL of sterile water (using a 60 mL oral syringe) given that no data exists as to whether naloxegol may bind to enteral nutrition. Given that naloxegol (or matching placebo) is formulated as an easily crushed, film-coated tablet, the bedside nurse will crush the naloxegol (or matching placebo) tablet, mix in 60 mL of sterile water and draw up the contents (of the medication and sterile water) in a 60 mL oral syringe and administer via the gastric or enteral tube over 3-5 minutes. The bedside nurse will rinse the vessel used to crush the medication with another 30mL of sterile water, draw up the contents into the oral syringe and administer over 3-5 minutes. Tube feeds will then be restarted at the same pre-dose rate (i.e., if the patient was receiving tube feeds at the time of the study dose) one hour after the study drug dose is administered. This is a method of administration of enteral drug administration that has been used in other ICU clinical studies where data on the enteral administration of the crushed tablet does not exist.

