There are many potential sources of bias in study that investigating the efficacy of safety of naloxegol for the prevention of lower GI tract paralysis in critically ill adults and thus a double-blind, placebo-controlled study is the gold standard study design to use. There is no reason to suggest that a dose of greater than 25mg daily of naloxegol (the current FDA-approved dose for the treatment of opioid induced constipation) is not the appropriate dose for this pilot investigation. As outlined in the current package insert, the study dose will be reduced to 12.5mg daily when patients are concomitantly administered a moderate CYP314 inhibitor or who have renal dysfunction (calculated creatinine clearance \leq 60 ml/min). Given that this is a randomized study, the treatment and control groups should be identical. Initiation of docusate 100mg twice daily is a standard of practice in all patients receiving an opioid who are admitted to the medical ICU service at Tufts Medical Center. Given that it remains unknown if naloxegol is efficacious in preventing lower GI tract paralysis in critically ill adults and that half the patients will be administered placebo, all patients will be managed with an aggressive standardized laxative protocol that is based on the most common clinical practices in the ICUs at Tufts Medical Center.

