4.2 Exclusion criteria

- a. Scheduled use of morphine, oxycodone, hydromorphone, fentanyl \geq 100 mg morphine equivalents per day in the week prior to ICU admission as evaluated by medical record review and/or interview with patient and/or family.
- b. Scheduled use of methadone at any dose in the week prior to ICU admission as evaluated by medical record review and/or interview with patient and/or family.
- c. History of constipation (as defined by the scheduled use of bisacodyl, senokot, lactulose, PEG 3350 (Miralax) and/or Fleet enema) prior to ICU admission as evaluated by medical record review and/or interview with patient and/or family.
- d. Current scheduled use a medication affecting gastric motility (i.e., metoclopramide, domperidone, erythromycin and loperamide).
- e. Current use of medication known to be a strong CYP3A4 inhibitor (itraconazole, lopinavir/ritonavir, clarithromycin, ritonavir, ketoconazole, indinavir/ritonavir, voriconazole, nefazodone).
- f. Current use of a medication known to be a strong CYP3A4 inducer (rifampin, carbamazepine, St. John's Wort).
- g. Known serious or severe hypersensitivity to naloxegol (Movantik) or any of its excipients.
- h. Patients admitted with a history of a neurologic condition that may affect the permeability of the blood-brain barrier (e.g. multiple sclerosis, recent brain injury, Alzheimer's disease, uncontrolled epilepsy, acute stroke, acute meningitis).
- i. Patients admitted with an acute GI condition (e.g., clinical evidence of acute fecal impaction/complete obstruction, acute surgical abdomen, acute GI bleeding).
- j. Patients with a condition affecting GI motility or function (e.g. inflammatory bowel disease requiring immunosuppressive therapy, symptomatic Clostridium difficile, active diverticular disease, surgery on the colon or abdomen within 60 days of ICU admission).
- k. Patients with underlying cancer who are at heightened risk of GI perforation such as those with underlying malignancies of the GI tract or peritoneum, recurrent or advanced ovarian cancer, vascular endothelial growth factor inhibitor treatment.
- l. Current use of total parenteral nutrition
- m. Administration of enteral nutrition through a jejunum tube.
- n. Severe hepatic dysfunction

Drug Substance: Movantik
Study Number: ESR-15-11000
Tufts IRB #12043
Version: Protocol version #19
Date: September 10, 2018

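### Both dose-increase notes in Protocol section 5.5.2 order 25 mg when one trigger resolves without checking the other, contradicting the either/or rule for 12.5 mg

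*Protocol*

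**What the plan says.** The base rule appears in three places.

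- Protocol section 5.5.2, treatment arm: the 12.5 mg dose "will be administered in the following two situations", namely (a) current use of a moderate CYP3A4 inhibitor at any dose, and (b) calculated creatinine clearance of 60 ml/min or lower.
- Protocol section 3.2: "the study dose will be reduced to 12.5mg daily when patients are concomitantly administered a moderate CYP314 inhibitor or who have renal dysfunction".
- Protocol section 5.5.2, control arm: "A lower placebo dose of 12.5mg will be used for either of the above situations".

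The notes in section 5.5.2 then cover changes during the study.

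- Renal note: clearance is recalculated each day. A fall to 60 ml/min or lower moves the patient from 25 mg to 12.5 mg. The increase sentence begins "For a patient whose creatinine clearance improves to" 60 ml/min or more, and directs a rise to 25 mg.
- Inhibitor note: starting a moderate inhibitor reduces the dose to 12.5 mg. If such a drug "is stopped during the period of study drug administration then the study drug dose will be increased to 25mg daily", effective the day after it is stopped.

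Neither increase sentence mentions the other trigger.

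**The concern.** The base rule depends on two conditions, and 25 mg is appropriate only when both are absent. Each increase note looks at one. Read literally, two kinds of patient would be moved to the strength that the base rule withholds from them: a patient still at or below 60 ml/min whose inhibitor is stopped, and a patient still on an inhibitor whose clearance recovers.

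What is at stake is drug exposure in the naloxegol arm. The protocol's reason for the renal rule is that some patients with clearance at or below 60 ml/min "who were exposed to naloxegol 25mg daily were shown to exhibit markedly higher systemic exposure", by a mechanism it describes as not understood. It also says that a moderate inhibitor may raise serum concentrations. Neither trigger is presented as rare. Of reduced clearance it says that "this population represents more than 50% of the medical ICU population", and it describes many moderate inhibitors as heavily used in the ICU. The notes exist because both conditions are expected to change during the stay.

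**Working it through.** **Consistency check.** There is no plan figure to reproduce. The base rule and the increase notes can be set side by side for each way a single trigger can resolve.

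| Event | Other trigger | Base rule | Increase note | Agree? |
|---|---|---|---|---|
| Clearance rises above 60 | Inhibitor still in use | 12.5 mg | 25 mg | No |
| Clearance rises above 60 | No inhibitor | 25 mg | 25 mg | Yes |
| Inhibitor stopped | Clearance still 60 or lower | 12.5 mg | 25 mg | No |
| Inhibitor stopped | Clearance above 60 | 25 mg | 25 mg | Yes |

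Two of the four cases conflict, one from each note.

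**Does the daily clearance calculation repair it?** Not as written. The renal reduction is triggered by a fall to 60 ml/min or lower and is described as a step down from 25 mg. A patient whose clearance was already at or below 60 when the inhibitor stopped has had no fall, so the note does not bring the dose back down.

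**A related overlap.** A clearance of exactly 60 ml/min meets both the reduction condition (60 or lower) and the increase condition (60 or higher).

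**How many patients?** The documents do not permit a calculation, so this is an illustration.

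Inputs from the documents:

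- 18 patients in the naloxegol arm (section 3.1).
- At most 10 dosing days (section 5.8.1).
- Clearance of 60 ml/min or lower in more than 50% of the medical ICU population (section 5.5.2). This describes the unit, not the enrolled sample; 0.50 is used below.

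Assumptions, not in the documents:

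- 10% to 30% of patients receive a moderate inhibitor, independently of renal function.
- Among patients with both triggers, exactly one resolves during dosing in 10% to 50%.

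Expected number with both triggers = inhibitor rate × 0.50 × 18:

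- Low: 0.10 × 0.50 × 18 = 0.9
- High: 0.30 × 0.50 × 18 = 2.7

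Expected number meeting the conflicting instruction = number with both triggers × proportion in whom exactly one resolves:

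- Low: 0.9 × 0.10 = 0.09
- High: 2.7 × 0.50 = 1.35
- Mid-range: 0.20 × 0.50 × 18 × 0.30 = 0.54

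Section 4.2 excludes patients with "Current scheduled use a medication affecting gastric motility", and its list includes erythromycin, one of the four moderate inhibitors named in section 5.5.2. That favours the lower end.

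**The case against.** The strongest defence is that the section can be read as a whole. The base rule is written in terms of the patient's current state and is not confined to the first dose. Clearance is available every day, and the either/or wording appears both before the notes and after them, in the control-arm text. The renal reduction starts from 25 mg, which suggests that the notes were drafted with single-trigger patients in mind. On that reading they omit a cross-reference and do not set a competing rule. A careful pharmacist would probably keep such a patient on 12.5 mg, and the investigational pharmacy packages every dose. The reading is plausible, but nothing in the protocol makes it the governing one. The notes are the more specific text for mid-study changes and are worded as mandatory, so staff who follow them literally are following the protocol.

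The second argument is that harm is neither quantified nor unguarded. The package-insert statement concerns a starting dose and reports higher exposure in only some patients; the inhibitor warning says only that concentrations may rise. Withdrawal is scored before and 2 hours after each dose, diarrhea has a hold-and-stop rule (section 5.8.1), and the principal investigator or the patient's physician can stop the drug (sections 5.8.1 and 6.4.2). This largely stands and limits the severity. It does not remove the point: section 3.1 says that the withdrawal score cannot be collected during deeper sedation, although such periods are expected to be short, and the diarrhea rule acts only after the event. The daily forms in Appendices 9 and 10 have no field for inhibitor use or tablet strength, so they would not by themselves reveal a mismatch, although the package label does carry the strength.

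The third argument is that the patient count rests mostly on assumed inputs. That is correct, and the count should be read only as an indication that few patients are involved. The number actually given the wrong strength would be smaller still if staff apply the either/or rule.

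**Conclusion.** The concern holds. Both increase notes, as written, direct 25 mg in a state for which the same section prescribes 12.5 mg, and no text settles the conflict. It arises only in a patient who has both triggers and then loses exactly one within at most 10 dosing days. Under the stated assumptions that is about 0.1 to 1.4 of 18 naloxegol patients, so probably one or fewer. The inhibitor rate, the resolution rate and independence are all assumed.

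The two-of-four conflict rests on the text alone and is firm; the patient count is not. The consequence is possible higher exposure to a drug at its approved dose, under monitoring. Blinding, the primary analysis, alpha, power and the sample size are untouched. This is a minor patient-safety correction that should be made.

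**What to change.** Amend both increase notes in section 5.5.2, and any pharmacy dosing sheet based on them, to a single condition: increase to 25 mg only when no moderate CYP3A4 inhibitor is in use and creatinine clearance is above 60 ml/min; otherwise remain on 12.5 mg. Keep the existing day-after timing when an inhibitor is stopped, and apply the same wording to placebo.

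This carries the protocol's own either/or rule into the notes and makes rule and notes agree in all four cases in the table. Setting the increase threshold above 60 matches the base rule, which gives 12.5 mg at exactly 60, and so also removes the overlap there.

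The cost is one clause in each of two notes and a matching edit to any dosing sheet. It adds no patients, procedures or data and does not affect blinding.
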